8.8.3 LABORATORY DATA

As chemistry and hematology data are only processed by the local laboratories, summary tables for these parameters will not be created. Shift table from baseline to each visit (as well as to the worst grade) will be prepared for all parameters with NCI CTCAE grades. Separate summaries will be created for the number and proportion of subjects with Grade 3 or worse toxicity for each parameter.

All chemistry and hematology values will be listed, together with their NCI CTCAE grades. Clinically significant abnormalities will be flagged. Pregnancy test results will be listed.

8.8.4 VITAL SIGNS AND OTHER SAFETY PARAMETERS

Vital signs (SBP and DBP, heart rate, respiratory rate, and temperature), Karnofsky Performance Score, and body weight will be summarized for each treatment group at each visit using descriptive statistics. Summary statistics (n, mean, median, SD, minimum, and maximum) will be calculated for both the actual value and the change from baseline value at each scheduled visit. A listing of vital signs will also be created.

Tumor response assessments (based on RECIST or other standard criteria used at the investigational site) at each timepoint following the last dose of CRT (3, 6, and 12 months) will be listed for individual subjects and tabulated in frequency tables, by treatment group.

Physical examination results both at baseline and at the end of the treatment will be summarized. Individual subject listings of physical examinations will be prepared as well.

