3 STUDY DESIGN

This is a Phase 2, double-blind, placebo-controlled, 2-arm, multi-center trial in which subjects will be randomized in a 1:1 ratio to receive either placebo or AG013.

AG013 has already been studied in healthy volunteers and in subjects experiencing OM during induction CT for the treatment of head and neck cancers. This is however the first time AG013 will be administered to subjects with cancers of the head and neck receiving concomitant CRT. To protect subjects from unanticipated safety risks, enrollment and treatment in the double-blind study will continue until 10 subjects on AG013 have been recruited. The DSMB will review safety data after these 10 subjects on AG013 have

This document contains confidential information. It is intended solely for the use of the principal investigator, co-investigators, staff, appropriate institutional review boards or ethical committees, and other required regulatory bodies.

- - - - -

completed study treatment. If there are no safety signals identified, the study will continue to recruit the planned number of subjects.

There are 4 study periods as described below: screening, active treatment, short term follow-up and long term follow-up. The screening phase will be no longer than 4 weeks. The active treatment phase will be between 7 and 9 weeks depending on the subject's prescribed CRT plan. The short term follow-up phase will be 4 weeks in duration. The long term follow-up will continue until 12 months post CRT. Oral mucositis (OM) assessments will begin at the start of CRT and continue until the subject has completed short term follow-up or until the OM resolves (as defined by a score of \leq 1 based on WHO criteria), whichever comes first. Long term follow-up will continue for 12 months to assure that AG013 does not adversely impact the tumor response to anti-neoplastic therapy.

A subject's Investigational Medicinal Product (IMP) treatment assignment (AG013 or placebo) will be randomized 1:1 as follows:

- Arm A: Placebo tid
- Arm B: AG013, 2 x 10¹¹ CFU/15 mL tid

. . . .

Table 1	Study Periods
Saraaning Dhasa	Within 4 weeks prior to randomization
Screening I hase	(Assessment of initial eligibility for study participation)
Active	Start: Day 1 of CRT
Treatment	Completion: Day 14 Post CRT
Phase	Duration: 7 to 9 weeks depending on the duration of CRT
	Start: Day 15 Post CRT
	Completion: Day 42 Post CRT (± 3 days)
Short Term	Duration: 4 weeks

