Clinical laboratory data will be presented for each treatment group using descriptive statistics based on the observed values and change from baseline values at each scheduled visit. Summary statistics (n, mean, median, SD, minimum, and maximum) will be calculated for quantitative safety data and frequency counts will be compiled for classification of qualitative safety data. Shift tables from baseline to the worst post-baseline values during the treatment period will be provided for chemistry parameters and hematology parameters that have NCI-CTCAE v4.03 toxicity grades. Both scheduled and unscheduled post baseline values during the treatment period will be considered. Additionally, the number and percentage of subjects with Grade \geq 3 will be presented for each CTCAE gradable laboratory test.

All clinical laboratory data will be listed by subject. Values outside the normal ranges will be flagged and toxicity grades will be displayed for relevant parameters.

To assess IMP tolerability, average daily ratings of IMP taste, consistency, and smell will be summarized descriptively, by week, for each treatment group.

Pre-study abnormalities and reported abnormalities at the end of active treatment will be tabulated by body system. Changes in physical examinations will be described in the text of the final study report.

Prior and concomitant medications will be coded using the WHO dictionary. These data will be tabulated for each treatment group; details regarding dose regimens and start/stop dates will be presented in by-subject data listings.

The number and percentage of subjects with presence of AG013-sAGX0085 bacteria will be summarized by treatment group.

Tumor response assessments will be summarized descriptively at each timepoint (3, 6, and 12 months following the last dose of CRT).

This document contains confidential information. It is intended solely for the use of the principal investigator, co-investigators, staff, appropriate institutional review boards or ethical committees, and other required regulatory bodies.

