8. ANALYTICAL PLAN AND STATISTICAL METHODS

8.1 GENERAL CONVENTIONS AND STATISTICAL CONSIDERATIONS

All statistical analyses will be performed and data appendices will be created using the SAS system version 9.4 or higher.

Summary statistics for continuous variables will include number of patients with nonmissing values, number of patients with missing values, mean, standard deviation, median, Q1 (quartile 1), Q3 (quartile 3), minimum and maximum values.

Summary tables for categorical variables will include number and percentage of patients for each category. If not specified additionally, number of patients with non-missing values will be the denominator for percentage calculation. The number of patients with missing values will be presented.

All the analyses will be run displaying by treatment arm and overall.

Unless otherwise stated, all statistical tests will be performed using two-sided tests at the 5% significance level.

If necessary, the statistical analytical plan and statistical methods section may be updated before the database lock. Any changes in statistical methods that may have an impact on the primary conclusions drawn from this clinical trial will be described in an amendment to the protocol. All other changes in the statistical plan will be described in section 9.8 of the clinical study report (CSR). An explanation will be provided for deviations from the planned analysis.

After the last subject completes the end of the short term follow-up phase the database will be locked and the study will be unblinded for the purpose of the statistical analysis. Evaluation of all efficacy and safety endpoints will occur. Evaluation of PK and PD endpoints will occur at a later stage, as well as the genomic analyses. Note: the PD and genomic analyses will only be performed if the study has a positive efficacy outcome. The overall tumor response to chemoradiation therapy will be evaluated following the second database lock after the last subject completes the long term follow-up phase (i.e. 12 months after the last dose of CRT).

A full study report will be written after completion of the statistical analysis including the evaluation of the efficacy and safety endpoints as described in Section 10.1. The PK data and overall tumor response to chemoradiation therapy will be described in an addendum to the study report, as well as PD endpoints and genomic analyses (in case of positive primary endpoint) after (a) later database lock(s).

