8.3 HANDLING OF MISSING DATA

All available efficacy and safety data collected for the study will be included in data listings and/or summary tables. Every effort will be made to obtain required data at each scheduled evaluation from all subjects enrolled. Rules for deriving efficacy endpoints will utilize imputation rules as specified in the efficacy analysis section. Sensitivity analyses will be performed to ensure that results of the primary efficacy endpoint are robust and not explained by missing or incomplete data. Worst-case assumptions will be applied to subjects who do not have OM assessments during the study period. Where necessary, missing assessments of OM will be imputed using multiple imputation procedures. Select exploratory sensitivity analyses will be conducted to ascertain the effect, if any, of these methods. No other missing data will be imputed.

Any imputation of missing or incomplete data will be flagged in the analysis data sets. The original value will be kept for traceability.

Incomplete dates imputation.

The following rules will be applied for AEs and concomitant medications with incomplete dates:

- If Day is missing for Start Date and Month and Year are the same as Month and Year for the First Dose of IMP Date, then Start Date equals First Dose of IMP Date.
- If Day is missing for Start Date and Month and Year are not the same as Month and Year for the First Dose of IMP Date, then impute Day 1 of the Month.

- If Day and Month are missing for Start Date and the Year is the same as the Year for the First Dose of IMP Date, then Start Date equals First Dose of IMP Date.
- If Day and Month are missing for Start Date and the Year is less than Year for the First Treatment Date, then impute July 1st of the Year.
- If Day and Month are missing for Start Date and the Year is greater than Year for the First Treatment Date, then impute January 1st of the Year.
- If the entire Start Date is missing, set it equal to First Dose of IMP Date.

No imputation for the end date of AEs will be done. However, the end date of concomitant medications will be imputed as the last day of the month if only the day is missing, and as December 31st of the year if both the day and the month are missing. The above imputation is needed to properly identify treatment-emergent adverse events (TEAEs) and prior/concomitant medications.

Other missing data imputation.

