8.8.2 ADVERSE EVENTS

All AEs will be coded by PT and SOC using MedDRA version 19.0 or higher. The NCI-CTCAE (Version 4.03) will be used to grade both clinical and laboratory AEs.

The incidence of TEAEs will be summarized by treatment group and tabulated by SOC and Preferred Term (PT). A TEAE is defined as an AE that first occurs or worsens in severity on or after the first dose of the IMP until end of short term follow-up. Summary tables will include all TEAEs. Incomplete starting dates of AEs will be imputed using the rules from section 8.3 of this SAP. TEAEs will be further summarized by severity (grade) and relatedness to IMP. Each AE (based on PT) will be counted only once for a given

subject. If the same AE occurs on multiple occasions, the highest severity and strongest relationship will be assumed. If 2 or more AEs are reported as a unit, the individual terms will be reported as separate events. AE severity will not be imputed if missing.

Summaries and by-patient data listings of TEAEs, AEs leading to death, SAEs, and AEs leading to discontinuation will be provided. The by-patient AE data listings will include onset and resolution dates, verbatim term, PT, treatment, severity (grade), relationship to treatment, action taken for the event, and outcome. All the deaths, including those reported during the long-term follow-up period, will be listed with the primary causes.

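### The 12-month tumour safety endpoint has no rule for counting death or earlier progression and no cumulative or between-arm estimate, so its tabulated percentages can understate a difference

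*SAP*

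**What the plan says.** Protocol 3 gives the purpose: "Long term follow-up will continue for 12 months to assure that AG013 does not adversely impact the tumor response to anti-neoplastic therapy". Overall tumour response over the 12 months after CRT is a named safety endpoint (Protocol 10.1.3, SAP 5.3). Protocol 6.4 has progression, second primaries, additional malignancies and survival collected at months 3, 6 and 12, by RECIST or the site's own standard.

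The analysis is brief. Protocol 10.6: "Tumor response assessments will be summarized descriptively at each timepoint (3, 6, and 12 months following the last dose of CRT". SAP 8.8.4 adds that the assessments "will be listed for individual subjects and tabulated in frequency tables, by treatment group". SAP 8.8.4 gives no denominator of its own, so SAP 8.1 applies: "If not specified additionally, number of patients with non-missing values will be the denominator for percentage calculation". The same section adds: "The number of patients with missing values will be presented". SAP 8.3 imputes OM assessments and incomplete dates and then closes: "No other missing data will be imputed".

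Two other outputs bear on the question. SAP 8.8.2: "All the deaths, including those reported during the long-term follow-up period, will be listed with the primary causes". SAP 8.4 counts deaths by planned arm and overall, without stating the data cut.

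The treatment codes are opened at the first lock, once the last subject finishes short-term follow-up. The tumour endpoint is evaluated after a second lock (Protocol 9, SAP 8.1).

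**The concern.** The question is about a period: did more AG013 subjects progress or die within 12 months? The planned tables describe three separate days. At month 12, a subject who died at month 5 may be a non-missing category or may be missing; the SAP does not say which. A subject who progressed at month 3 may be shown by status at the month-12 visit or as having progressed; that is not stated either. If such subjects have no month-12 value, the default denominator leaves them out, and the percentages describe only those still assessed.

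The other safety tables do not fill the gap. Routine recording of adverse events ends with short-term follow-up (Protocol 8 and 8.8), and so does the treatment-emergent window (SAP 8.8.2). The tables in SAP 8.8.4 are therefore the only planned by-arm summary of progression.

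Timing matters too. A counting rule chosen after the first lock would be chosen with the arms known.

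**Working it through.** **No figure to reproduce.** The documents give no expected rate, event count, margin or power for this endpoint. Every event rate and missing share below is an assumption.

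**Inputs.** About 200 subjects at 1:1 (Protocol 4.1 and 5.9), so N = 100 per arm. Percentages over non-missing subjects (SAP 8.1). Assumed: E subjects per arm with progression or death by month 12, and a share s of them, equal in both arms, with no month-12 record. Everyone else is assessed and event-free.

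**Step 1: what the table shows.** Tabulated event-free percentage = (N − E) / (N − sE). With E = 20 (placebo) and 30 (AG013), the true gap is 10 points.

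- s = 0: 80/100 = 80.0% against 70/100 = 70.0%; gap 10.0. Missing: 0 and 0.
- s = 0.5: 80/90 = 88.9% against 70/85 = 82.4%; gap 6.5. Missing: 10 and 15.
- s = 1: 80/80 = 100% against 70/70 = 100%; gap 0. Missing: 20 and 30.

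**Step 2: other event rates, true gap still 10 points.**

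| Events, placebo / AG013 | Gap, s = 0 | Gap, s = 0.5 | Gap, s = 1 |
|---|---|---|---|
| 20 / 30 | 10.0 | 6.5 | 0 |
| 25 / 35 | 10.0 | 6.9 | 0 |
| 30 / 40 | 10.0 | 7.4 | 0 |

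The result depends mainly on s, which the documents neither give nor control by a rule. Shares that differ between arms could shrink the gap further or widen it.

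**Step 3: what a better analysis could deliver.** For 20% against 30% with 100 per arm and complete data, the standard error of the difference is √(0.2×0.8/100 + 0.3×0.7/100) = √0.0037 = 0.061. The 95% CI is 10 ± 1.96 × 6.1, about −2 to 22 points.

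For a hazard ratio with D events in total, the 95% limits are the HR divided and multiplied by exp(1.96 × 2/√D): 2.40 at D = 20, 1.74 at D = 50 and 1.60 at D = 70. In the example D = 50 and, under proportional hazards, HR = ln 0.70 / ln 0.80 = 1.60, so the interval runs from 1.60/1.74 = 0.92 to 1.60 × 1.74 = 2.78. By Schoenfeld's formula, 80% power at two-sided 5% for HR 2.0 needs 4(1.96 + 0.84)²/(ln 2)², or 66 events; HR 1.5 needs 191.

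**The case against.** The strongest reply is that nothing is concealed. The missing counts must be printed, so in the half-missing case a reader sees 10 against 15 beside the percentages. Every long-term death is listed with its cause, deaths are counted by arm, tumour data are listed by subject, and an addendum after the second lock carries updated safety information (Protocol 12.10). This stands. A reader might infer that deaths and early progressors vanish and that harm can be hidden, but the documents do not support that. Progression is not among the reasons for removal in Protocol 4.4, and Protocol 6.4 has it recorded at each visit, so a subject who progresses and attends stays in the table. Survival is part of the tumour status data, so death could be a recorded category. The eCRF and the mock tables announced in SAP 2 may settle this; neither was available.

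Second, protocol and SAP agree on descriptive summaries, and the endpoint is called tumour response, not progression-free survival. That is so; the point is not an inconsistency.

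Third, a time-to-event analysis would not settle the question either. Step 3 confirms this: the example's interval includes no harm.

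What remains is that none of the planned outputs joins death to progression, gives a cumulative proportion or attaches an interval. The reader would have to assemble the answer from listings after unblinding.

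**Conclusion.** The concern holds in a limited form. The SAP leaves open how death and earlier progression are counted at later visits, defaults to a non-missing denominator, and plans no cumulative or between-arm estimate for an endpoint whose purpose is to give assurance about tumour control. The percentages can therefore understate a difference: a true 10-point gap shows as 10.0 points with complete month-12 records, 6.5 to 7.4 with half of those with events unrecorded, and 0 with all unrecorded. These sizes rest on assumed event rates, an assumed missing share equal in both arms, and 100 subjects per arm. The zero-gap case is an extreme, not a forecast. It also does not follow that the fix would demonstrate safety; it would give an honest estimate with wide limits.

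**What to change.** Amend SAP 8.8.4 before the first-lock unblinding.

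- **Denominator and categories.** At months 3, 6 and 12, use all SAF (or all randomised) subjects due at the visit, including those who have died or been lost. Show death, prior progression and missing as separate categories.
- **Cumulative estimates.** By arm, give the proportion with progression or death, and with death, by months 3, 6 and 12, with the between-arm difference and 95% CI.
- **Timing.** Where event dates exist, use Kaplan-Meier curves and a hazard ratio with CI. Otherwise use visit-interval timing. Stratify only if the cells allow it: three binary factors make up to eight strata.
- **Label.** Call it estimation, not a powered test.
- **Death count.** State the data cut for the SAP 8.4 count and repeat it at the second lock.

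The cost is SAP wording and a few outputs at the second lock. The status data are already planned. Whether exact progression and death dates are captured is not stated and should be checked first. The downside is precision: the hazard ratio limits will be a factor of about 2.4 either way at 20 events, 1.7 at 50 and 1.6 at 70 (assumed counts). The interval may not exclude harm, and progression criteria differ by site. The report should say so.

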8.9 OTHER ENDPOINTS AND ANALYSIS

8.9.1 PHARMACOKINETICS, PHARMACODYNAMICS AND GENOMICS

The PK analysis will be performed at Precigen ActoBio (formerly Intrexon Actobiotics), and individual outcomes per patient per visit will be derived. PK parameters will be calculated by summarizing the parameters and concentrations by visit. Analysis will be descriptive, no hypothesis testing will be performed. Listings for PK data will be created as well.

Blood and buccal smears will be collected at specific time points in a subset of subjects who consent separately (targeting 15 subjects on AG013 and 15 subjects on placebo). Descriptive summary statistics will be used to evaluate the pharmacokinetics of AG013 by treatment group and study visit. Blood levels of AG013-sAGX0085 bacteria, serum levels of hTFF1 and buccal mucosa levels of AG013 (both AG013-sAGX0085 bacteria and hTFF1) will be summarized using descriptive statistics, including graphical methods.

Biomarker assessments will be listed and summarized for each treatment group by time point using descriptive statistics (mean, median, SD, SEM, coefficient of variation, minimum, and maximum) and graphical displays. The relationship between biomarkers and efficacy outcomes will be explored via correlation analysis, as appropriate. Note: this analysis will only be performed in case of a positive outcome on the study regarding the efficacy outcome, i.e. positive primary endpoint.

PD (biomarker) and Genomic analyses will be described in a separate plan.

Note: PD (biomarker) and Genomic analyses will only be performed in case of a positive efficacy outcome on the study.

9. DEVIATIONS FROM ANALYSIS AS DESCRIBED IN THE PROTOCOL

Per protocol, baseline characteristics and demography data should only be summarized for SAF population. We have added these summaries for ITT population as well, to support the primary analysis.

The protocol stipulates that laboratory data should be summarized using the usual set of descriptive statistics at each visit, both for actual values and changes from baseline. However, as hematology and chemistry data are only collected locally in this study, these summaries were replaced with shift tables for NCI CTCAE grades.

The Protocol states regarding Severe OM Incidence that subjects with no OM assessments will be assumed to have severe scores and subjects who die or withdraw without experiencing OM grade 3 or 4 will also be assumed to have severe scores. This will not be done in incidence analyses.

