To ensure that primary efficacy results are robust, sensitivity analyses will be performed using alternative methods for the analysis of duration of severe OM in both the ITT, mITT and PP populations. These methods will include calculations based on the number of days with grade 3 or 4 mucositis throughout the active treatment phase (from start of CRT until 14 days after completing CRT), and the use of various imputation strategies for gap days (i.e., days between twice weekly assessments). In particular, imputation of last observation carried forward and worst-adjacent values will be employed for subjects with missing or incomplete data.

Secondary Efficacy Endpoints:

Statistical methods for the calculation and analysis of secondary efficacy endpoints are provided below. For each endpoint, significance testing will evaluate the superiority of AG013 compared to placebo; two-sided tests will be used to reject the null hypothesis (no difference between groups) in favor of the alternative hypothesis (there is a difference between groups). All efficacy analyses will be performed for the mITT population and stratified by randomization factors (region, cisplatin regimen and HPV status). To control the experiment-wise Type 1 error rate at 5%, significance tests will be performed in the hierarchical order listed here.

Time to onset of severe OM: Time to onset of severe OM (WHO grade 3 or 4) will be calculated as the elapsed time (in days) from the start of CRT until the date of first OM assessment grade 3 or 4. Subjects who do not experience an event by the end of the OM assessment period will be censored on the date of last OM assessment. Subjects with no post-baseline OM assessments will be censored on Day 1. Kaplan-Meier estimation methods and the stratified log-rank test will be used to compare time-to-event distributions and test whether or not AG013 delays the onset of severe OM.

Incidence of severe OM: The incidence of severe OM (WHO grade 3 or 4) will be calculated as the number of subjects with at least one OM WHO grade 3 or 4, divided by the number subjects in the treatment group. Subjects with no OM assessments will be assumed to have severe scores. Subjects who die or withdraw without experiencing OM grade 3 or 4 will also be assumed to have severe scores. A stratified CMH test (general association statistic) will

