8.7.2 ANALYSIS OF KEY SECONDARY EFFICACY ENDPOINTS

Statistical methods for the calculation and analysis of secondary efficacy endpoints are provided below. For each endpoint, significance testing will evaluate the superiority of AG013 compared to placebo; two-sided tests will be used to reject the null hypothesis (no difference between groups) in favor of the alternative hypothesis (there is a difference between groups). The analysis of all key secondary efficacy endpoints will be performed for the ITT, mITT and PP populations.

Note: The OM assessment period includes all OM Assessments performed, including the short-term follow-up period.

To control the experiment-wise Type 1 error rate at 5%, significance tests of the key secondary efficacy endpoints will be performed in the hierarchical order listed below. As specified in the protocol, the mITT population will be the main analysis and guide the hierarchical order of testing. To support these results, the same analyses will be repeated for ITT and PP populations. Each analysis will control for stratifications factors. All the analyses described below will be performed for the purpose of displaying summary statistics, but once the first in the sequence of tests yields a p-value that exceeds 0.05, the nominal p-value for this and subsequent endpoints in the series will be declared non-significant.

Time to onset of severe OM: Time to onset of severe OM (WHO grade 3 or 4) will be calculated as the elapsed time (in days) from the start of CRT until the date of first OM assessment grade 3 or 4. Subjects who do not experience an event by the end of the OM assessment period will be censored on the date of last OM assessment. Subjects with no post-baseline OM assessments will be censored on Day 1. Kaplan-Meier estimation methods and the stratified log-rank test will be used to compare time-to-event distributions and test whether or not AG013 delays the onset of severe OM. The log-rank test will be stratified by cisplatin regimen, HPV status and region. Below is the sample SAS code that performs the intended analysis:

```
proc lifetest
```

```
data=test;
time Time_to_Onset*censor(1);
strata CIS_GRP HPV REGION / group=TRTPN;
run;
```

Incidence of severe OM: The incidence of severe OM (WHO grade 3 or 4) will be calculated as the number of subjects with at least one OM WHO grade 3 or 4, divided by

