the number subjects in the treatment group. A stratified CMH test (general association statistic) will be used to compare proportions and test whether or not AG013 reduces the incidence of severe OM. Incidence will be calculated for two observation periods: (1) entire follow-up period, and (2) from the first to last day of CRT. Incidence of severe OM will also be summarized descriptively for subgroups defined by 3 factors (cisplatin regimen, region, HPV status) in the mITT population only.

Duration of ulcerative OM: The duration of ulcerative OM (WHO grade 2, 3 or 4) will be calculated in a manner similar to duration of severe OM. That is, the duration of ulcerative OM will be calculated as the number of days from the onset of ulcerative OM (first time a WHO grade 2, 3 or 4 is observed) to the day when ulcerative OM has resolved (first time WHO grade 0 or 1 is observed after last WHO grade 2, 3 or 4). An imputation scheme similar to the primary analysis will be used in the event that subjects discontinue prior to resolution of OM to grade 0 or 1. The stratified CMH test (with modified ridit scores) will be used to compare treatment groups and test whether or not AG013 reduces the duration of ulcerative OM.

Time to onset of ulcerative OM: Time to onset of ulcerative OM (WHO grade 2, 3 or 4) will be calculated and analyzed as described above for severe OM.

Incidence of ulcerative OM: Incidence of ulcerative OM (WHO grade 2, 3 or 4) will be calculated and analyzed as described above for severe OM.

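### The SAP drops the protocol's worst-case rule for OM incidence without a reason, so subjects lost before onset count as free of OM, and no sensitivity analysis shows the effect

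*SAP*

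**What the plan says.** Protocol 10.5, on incidence of severe OM, has two imputation rules. For subjects never examined: "Subjects with no OM assessments will be assumed to have severe scores". For early leavers: "Subjects who die or withdraw without experiencing OM grade 3 or 4 will also be assumed to have severe scores".

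SAP 9 restates both and cancels them: "This will not be done in incidence analyses". The other two deviations listed in SAP 9 each carry an explanation; this one does not.

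SAP 8.7.2 defines incidence as "the number of subjects with at least one OM WHO grade 3 or 4, divided by" "the number subjects in the treatment group". The numerator needs an observed grade 3 or 4, but the denominator keeps everyone. The method passes to the last key secondary endpoint: "Incidence of ulcerative OM (WHO grade 2, 3 or 4) will be calculated and analyzed as described above for severe OM".

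Three other parts of the SAP bear on this:
- SAP 8.7.2 states that "the mITT population will be the main analysis and guide the hierarchical order of testing", and SAP 7.3 admits to mITT only subjects with a dose and a post-baseline OM assessment.
- SAP 8.3 still promises worst-case handling of subjects without OM assessments, and multiple imputation where needed.
- The five sensitivity analyses in SAP 8.7.1 all concern the duration of severe OM.

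**The concern.** A subject who dies or leaves before onset has an unknown outcome. The protocol scores that subject as a failure; the SAP scores the same subject as a success. When loss before onset differs between arms, the SAP count lowers incidence more in the arm that loses more, with no drug effect needed.

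Incidence of severe OM is the second key secondary endpoint and has its own power statement. Incidence of ulcerative OM is the fifth. SAP 8.7.2 displays both results wherever the formal sequence stops, so a reader will see the difference and its p-value in any case. Nothing in the plan would show how far they depend on the scoring rule.

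In mITT the never-assessed rule has nothing to act on, because those subjects are already excluded. There the die-or-withdraw rule is what matters; the never-assessed rule matters in the ITT repeat.

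**Working it through.** **The plan's own figure.** Both documents state about 85% power for 75% v 50% with 80 per arm (Fisher's exact test, two-sided 5%). Exact enumeration gives 88.3%; about 74 per arm gives 85.6%. The stated figure is conservative and does not affect this point.

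**Inputs.** True incidence of 75% and 50% comes from SAP 6. The 100 per arm is the planned enrolment of about 200, split 1:1. Loss before onset, *d*, is assumed, because the documents give no drop-out by arm. The planned step from 200 enrolled to 160 evaluable implies 20% non-evaluable, but that is not the same as loss before onset. Lost subjects are given the same underlying risk *p* as the rest. The test is the unstratified 1-df CMH statistic, by exact binomial enumeration.

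**Formulas.** SAP count: p(1 − d). Protocol count: p(1 − d) + d.

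**No drug effect (p = 0.75 in both arms), AG013 v placebo**

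| Loss | SAP count | Test alone favours AG013 | Protocol count | Test alone favours AG013 / placebo |
|---|---|---|---|---|
| 20% v 10% | 0.75×0.80 = 60.0% v 0.75×0.90 = 67.5% | 19.2% | 80.0% v 77.5% | 0.8% / 6.1% |
| 20% v 5% | 60.0% v 0.75×0.95 = 71.25% | 38.3% | 80.0% v 76.25% | 0.4% / 9.1% |
| 10% v 5% | 67.5% v 71.25% | 8.2% | 77.5% v 76.25% | 1.5% / 3.9% |
| 10% v 20% | 67.5% v 60.0% | 0.1% | 77.5% v 80.0% | 6.1% / 0.8% |

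The nominal rate in each direction is 2.5%. An ordinary pooled z test gives 19.5% and 38.9% in the first two rows. For a 10-point gap in loss, the SAP count moves the difference by 0.75×10 = 7.5 points towards the arm losing more; the protocol count moves it by 0.25×10 = 2.5 points against that arm. With equal loss of 10% or 20% there is no bias and the two-sided error is about 5%.

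**Timing of loss.** The table puts all loss before onset. If loss is spread over days 1 to 49, with onset assumed uniform over days 14 to 49, simulated rates for the SAP count fall to about 11% (20% v 10%) and 18% to 20% (20% v 5%).

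**The testing sequence.** Incidence can be claimed only after duration and the log-rank test for onset are both significant, and the log-rank test censors early leavers. Simulating the first two rows with non-informative loss, incidence and log-rank together favour AG013 in about 1.9% to 2.4% of trials. Adding the duration gate, with assumed durations, gives 1.5% and 1.9%.

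**Planned effect (50% v 75%), chance of significance for AG013**

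| Loss | SAP count | Protocol count |
|---|---|---|
| none | 25 points, 95.9% | the same |
| 20% v 20% | 40% v 60%: 20 points, 82.6% | 60% v 80%: 20 points, 87.7% |
| 20% v 10% | 40.0% v 67.5%: 27.5 points, 98.0% | 60.0% v 77.5%: 17.5 points, 76.6% |
| 10% v 20% | 45.0% v 60.0%: 15 points, 58.6% | 55.0% v 80.0%: 25 points, 97.0% |

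**The case against.** The strongest reply is that the stand-alone rates are not error rates for any claim the plan allows. That stands. A reader might infer a 19% to 39% risk of a false incidence claim, but the fixed sequence does not support that: in the same scenario the log-rank gate holds it near the nominal 2.5%.

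The protocol rule is no neutral standard. It penalises the arm that loses more and, with equal loss, shrinks a real effect to the same 20 points. A reader might take a return to the protocol rule as the cure; the arithmetic does not support that either.

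The SAP change has a logic. SAP 8.7.1 gives zero days of severe OM to subjects never seen with it, even if not fully followed, so the new count agrees with the primary endpoint. But both then lean the same way under unequal loss. The mismatch between censoring for onset and full follow-up for incidence is partly inherited: the protocol also censored these subjects for onset while scoring them for incidence.

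Some checks exist. Protocol 6.3.1 requires an oral assessment on the day of withdrawal, which limits missed onsets. The PP repeat requires 50 Gy or an OM grade of at least 3, so it drops most subjects lost before onset. However, it selects partly on the outcome and is not a sensitivity analysis for this rule.

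Finally, the deviation is declared in SAP 9, so nothing is concealed.

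**Conclusion.** The point holds as a defect in estimation and reporting. SAP 9 reverses a protocol rule for two hierarchical endpoints without a reason, SAP 8.7.2 turns loss before onset into absence of OM, SAP 8.3 does not agree with SAP 9, and no named analysis shows the consequence for incidence.

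With no drug effect, a 10-point gap in loss before onset produces a false difference of 7.5 points, and a 15-point gap (20% v 5%) produces 11.25. The incidence test alone then favours the arm losing more in about 19% and 38% to 39% of trials, or fewer if loss is spread over time. These figures rest on assumed loss rates, 75% incidence, 100 per arm and lost subjects at the same risk as others.

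The documents do not show that AG013 will lose more subjects, so a bias towards the drug cannot be inferred; with the loss reversed, so is the bias. Protection of the formal claim was computed for non-informative loss and no effect on onset. It weakens if leaving is related to imminent severe OM.

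**What to change.** Keep the stratified CMH test on the SAP's observed-case count. In SAP 8.7.2, for severe and for ulcerative OM incidence, in mITT and ITT:

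- add a named sensitivity analysis that applies the protocol's worst-case count, shown beside the observed-case count, so that readers see the result under both scoring rules;
- add a supportive difference in 1 minus the Kaplan-Meier estimate at one fixed study day, from the time-to-onset data already derived. The end of the active phase will not serve, because it varies from 7 to 9 weeks.

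In SAP 9, state why the protocol rule was dropped. Reconcile that text with the worst-case and multiple-imputation promises in SAP 8.3.

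The cost is SAP wording and a few extra table rows, with no new data. The Kaplan-Meier estimate assumes that leaving, including death, is unrelated to imminent severe OM. When that holds it performs well: in simulation with all loss before day 14 it favoured AG013 in 2.7% (20% v 10%) and 2.2% (20% v 5%) of trials with no drug effect, and it recovered the 25-point difference under 20% loss in both arms. When it does not hold, the worst-case and observed-case rows still show how much the result depends on the subjects who left.
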